The treating physician will determine if their patient fulfills inclusion criteria. If they do, the physician will approach the patient and family to see if they are willing to discuss the study with a member of the study team. If they agree, a member of the study team will determine if the patient is eligible for the study, and if they are, they will then approach the patient and family to discuss the study and obtain consent. The consent and assent process will be conducted in the patients primary language (English or Spanish only). Patients who are eligible for the study and have provided consent/assent will first have their pain intensity measured within 15 minutes prior to receiving the IN hydromorphone (baseline assessment). They will be monitored as per standard practice by the health care providers in the emergency department for patients receiving an opioid analgesic (i.e. pulse oximetry, interval vital signs including blood pressure). All pain assessments will be performed using the Faces Pain Scale – Revised (FPS-R) and verbal Numeric Rating Scale (vNRS) by a research assistant, coordinator or study team physician. A nurse will administer the IN hydromorphone using a mucosal atomization device: this is Time 0. Immediately after the medication is administered, the patient will be asked to report how much pain or discomfort they experienced with the administration (also using the FPS-R and vNRS). The patient will have their pain assessed at the following time points: 5 minutes, 15 minutes, 30 minutes, 45 minutes, 60 minutes, and then every 30 minutes thereafter until 6 hours, the patient is discharged from the emergency department, or a non-IN hydromorphone rescue analgesic is administered (see following paragraph regarding first and second rescue medication assessments at 15- and 30-minutes). This non-IN hydromorphone rescue analgesic will be considered after 60 minutes, and its administration will be determined at the discretion of the primary attending physician. If a non-IN hydromorphone rescue analgesic is administered, the time when it

was given will be recorded. The attending physician may administer an analgesic of their choice as a rescue analgesic (e.g. IV hydromorphone, IV morphine) as per standard practice.

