At the 15- and 30-minute marks, the patient will undergo a first and second rescue IN hydromorphone assessment. They will be asked if their pain is, "much less, a little less, the same, or worse" compared to before they received the IN hydromorphone. If they reply, "the same", or "worse", they will receive an additional rescue dose of IN hydromorphone at 0.015 mg/kg, maximum single dose of 2 mg. We will also ask the patient, " "Do you want more medicine to make your pain less?", as patients who report that their pain is "a little less" or "a lot less" may still not have achieved adequate pain relief, and this deficit will not be identified without asking this specific follow-up question to confirm adequacy of pain relief. Intranasal hydromorphone has been shown to reliably produce adequate analgesia by 10 minutes when an adequate dose has been administered. Therefore, determining whether additional analgesia is required at 15 minutes is a reasonable amount of time to wait after administering a dose of IN hydromorphone to see if a patient experienced any improvement in pain intensity. This methodology has been used in prior pilot studies of analgesics, to prevent patients from receiving inadequate analgesia if the initially selected dose was not sufficient, and so that an effective dose can be determined. In addition, administering additional reduced doses (i.e. half initial dose) after 15 minutes of receiving a dose of parenteral opioid analgesic, if there has been no improvement in pain intensity, is standard practice when administering IV opioid analgesics as part of typical clinical care when treating pain in children.

Adverse events will be assessed and recorded by the research assistant or study investigator, in conjunction with the nursing staff and treating physician. These adverse events will include those considered minor and major. The specific adverse events being assessed are detailed on pages 8 and 9 of the data collection form. All adverse events will be assessed every hour.

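### Hourly adverse-event checks leave the 5- to 45-minute contacts unused for brief self-reported symptoms, and one pooled proportion per event separates neither IN dose number nor non-IN rescue

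*Combined protocol and SAP*

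**What the plan says.** All of this is in the combined protocol and SAP.

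- **Adverse-event schedule (Study Procedures).** "All adverse events will be assessed every hour". The starting point of the hour is not given. A research assistant or investigator records the events "in conjunction with the nursing staff and treating physician". The list of events is on pages 8–9 of a data form that is not among the documents.
- **Pain schedule (Study Procedures).** Pain is scored at "5 minutes, 15 minutes, 30 minutes, 45 minutes, 60 minutes, and then every 30 minutes thereafter until 6 hours", or until "the patient is discharged from the emergency department, or a non-IN hydromorphone rescue analgesic is administered". A research assistant, a coordinator or a physician on the study team does the scoring.
- **Repeat dosing (Study Procedures).** "At the 15- and 30-minute marks, the patient will undergo a first and second rescue IN hydromorphone assessment". A top-up may follow each of these, so a child may receive one, two or three IN doses.
- **Other early safeguards (Study Procedures).** Routine monitoring includes "pulse oximetry, interval vital signs including blood pressure". There is one question at dosing: "Immediately after the medication is administered, the patient will be asked to report how much pain or discomfort they experienced with the administration". It concerns the administration itself, not later drug effects.
- **Analysis (Statistical Procedures).** Adverse events are the secondary outcome, reported as the share of patients with each event type. Rescue times are recorded.
- **Per-patient review (Adverse Event Reporting).** The investigators evaluate adverse events for each patient once enrollment is complete.

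**The concern.** The Study Purpose and Rationale says that this route has not been studied in children, so tolerability is a main product of the pilot. Of the five events that Potential Risks lists as most common, three (bad taste, dizziness and nausea) are known mainly from what the child says. An oximeter or a blood pressure cuff does not record them. The Study Procedures also expect analgesia by 10 minutes after an adequate dose, so drug effects are expected early, in the period with no scheduled adverse-event question.

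Two things are at stake. A short-lived symptom may be forgotten, or placed at the wrong time, when a child in pain is first asked about it up to an hour later. And a single proportion per event cannot show whether the event followed one, two or three IN doses. It may also include events that followed another analgesic, because pain scoring stops at non-IN rescue and the text does not say whether adverse-event checks stop too.

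**Working it through.** **1. Contacts against checks.** Assume that the hourly clock starts at Time 0 and that no non-IN rescue is given. Pain contacts fall at 5, 15, 30, 45 and 60 minutes, then every 30 minutes from 90 to 360: 5 + 10 = 15. Adverse-event checks fall at 60, 120, …, 360: 6, each coinciding with a pain contact.

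| Stay | Pain contacts | Adverse-event checks | Contacts without a check |
|---|---|---|---|
| 1 h | 5 | 1 | 4 |
| 2 h | 7 | 2 | 5 |
| 3 h | 9 | 3 | 6 |
| 6 h | 15 | 6 | 9 |

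Before 60 minutes, 0 of 4 contacts has a scheduled check. The longest gap between scheduled enquiries is 60 minutes. On the pain schedule it would be 15 minutes in the first hour and 30 minutes after that. As an illustration, a child discharged at 55 minutes would have four pain contacts and no hourly check, though the per-patient evaluation and staff input would still apply.

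**2. IN exposure before the first check.** On the plan's own figures, below the single-dose caps: one dose 0.03 mg/kg; two doses 0.03 + 0.015 = 0.045 mg/kg; three doses 0.03 + 0.015 + 0.015 = 0.06 mg/kg. All may be given by about 30 minutes, so the first hourly check may follow any of the three totals.

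**3. Scale of one missed child.** With 40 patients, one child is 1/40 = 2.5 percentage points. At the rates quoted under Potential Risks, the expected counts are 40 × 0.21 = 8.4 for bad taste, 40 × 0.14 = 5.6 for dizziness and 40 × 0.06 = 2.4 for nausea.

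**4. What extra questions could gain (illustration only).** Assume that onset is uniform over 0–60 minutes, that a symptom lasting *d* minutes is recorded if present at an enquiry, and that a share *r* of symptoms already over is recalled. The documents give none of these inputs. If *h* is the chance of being present at an enquiry, capture is *h* + (1 − *h*) × *r*. For *d* = 10:

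- Hourly: *h* = 10/60 = 17%.
- Five contacts: *h* = (5 + 10 + 10 + 10 + 10)/60 = 45/60 = 75%.

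| Recall *r* | Hourly | Five contacts |
|---|---|---|
| 0 | 17% | 75% |
| 50% | 58% | 88% |
| 80% | 83% | 95% |
| 100% | 100% | 100% |

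The gain runs from 58 percentage points to nothing, depending on recall. With perfect recall, only timing improves. The model shows what the answer depends on; it does not estimate an under-count.

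**5. The tabulation.** The sentence beginning "If a non-IN hydromorphone rescue analgesic is administered, the time when it" secures the time of non-IN rescue, so events with a known onset can be placed before or after it. The planned analysis does not do this.

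**The case against.** The strongest reply is that nothing here is an error. No passage contradicts hourly assessment, and the planned outcome (ever affected, yes or no) needs no onset times. An hourly question that covers the preceding hour would serve it, and the unseen form may ask exactly that and record onset. This stands. It is why the point is an improvement and why no under-count can be claimed.

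Three stronger readings are tempting, and the documents support none of them.

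- A reader might infer that children go unobserved for an hour after an opioid. They do not: monitoring, vital signs and clinical staff input continue, and the investigators evaluate every patient's events.
- A reader might infer that onset times are not collected. The form that would settle this was not supplied.
- A reader might infer that top-up times go unrecorded. Statistical Procedures records the times of rescue analgesics, and Study Procedures calls the top-up a rescue dose, so the plain reading includes it.

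Two practical objections also stand in part. A coordinator may score pain but is not named as an adverse-event assessor, so a pain contact is not automatically a full adverse-event contact. And repeated prompting may raise reported rates or slightly influence the next pain score, which is the primary outcome.

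It can also be said that non-IN rescue is considered only after 60 minutes, so the first check would usually come before it. That does not help with later checks, and Potential Risks allows additional analgesics at any time.

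**Conclusion.** The point holds as a low-cost improvement to the secondary outcome. It is not a safety gap and does not threaten the primary outcome. Two weaknesses remain: less reliable capture and timing of brief self-reported symptoms, and a pooled proportion that can attribute events after another analgesic to IN hydromorphone and hides the number of IN doses received.

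The size can be stated only for the schedule: 4 unused contacts in the first hour and 9 over 6 hours. This rests on a clock that starts at Time 0. The effect on the event rates cannot be derived, because the documents give no symptom duration, onset pattern or recall period. If the form already captures the past hour and onset times, the first weakness largely disappears and only the tabulation point remains.

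**What to change.** - **Collection.** At each pain contact already scheduled, whoever scores the pain (research assistant, coordinator or study physician) asks a short set of self-report symptom questions covering the time since the last check, and records onset. The questions come after the pain scores. They neither condition nor delay any rescue treatment.
- **Hourly assessment.** Keep the full hourly adverse-event assessment with the staff now named for it, state when its clock starts, and continue it after pain scoring stops for non-IN rescue.
- **Reporting.** Report each event type overall, as planned. Add a descriptive table of events before and after non-IN rescue, and by number of IN doses received before onset. Use as denominator the children who reached each stage, and show events of unknown onset separately. Label the table non-randomised and sparse, because top-ups follow pain response.

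**Cost.** A small change to the form and one extra table, with no new visits. The time per contact is an assumption, 1–2 minutes. A 1-hour stay gains 4 × (1 to 2) = 4–8 minutes; over 40 children that is 160–320 minutes, or 2.7–5.3 staff hours. A 6-hour stay gains 9 × (1 to 2) = 9–18 minutes; over 40 children that is 360–720 minutes, or 6–12 hours. Reported rates may rise partly through prompting, and asking after the pain score limits but does not exclude an effect on the next one. Both should be acknowledged in the report. If the form already covers recall and onset, only the tabulation needs to change.

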Patients will receive IN hydromorphone (2 mg/mL concentration) at a dose of 0.03 mg/kg, maximum single dose 4 mg. This dose was obtained from prior studies demonstrating that the bioavailability of IN hydromorphone was 55%, and clinical studies showing that at least 4 mg was required to achieve clinically meaningful improvement in pain in adults, with no incidence of serious adverse events, and no significant difference in adverse events compared to lower doses. The usual pediatric dosing of IV hydromorphone is 0.015 mg/kg, so the use of 0.03 mg/kg is consistent with this demonstrated bioavailability of IN hydromorphone. In addition, other commonly-used IN analgesics and sedatives (e.g. fentanyl, midazolam, ketamine) are dosed in a similar fashion: that is, at least double (and for some medications, up to five times) the IV dose is used when administering the medication by the IN route. This dosing strategy and interpretation of the bioavailability and pharmacokinetic data for intranasal hydromorphone was discussed with [name] (Director of Biomarkers Core Laboratory of the Irving Institute for Clinical and Translational Research).

Statistical Procedures:

We will use descriptive statistics (mean/SD, median/IQR) to describe our patient population and their characteristics. Our primary outcome of median change in pain intensity will be measured using the Faces Pain Scale – Revised (FPS-R), a validated pain scale in children ages 4 to 17 years old, which allows a child to report their pain intensity on a scale from 0 (no pain) to 10 (most pain). Median change in pain intensity will also be measured using the verbal Numeric Rating Scale (vNRS), which assesses pain by asking how much pain they have on a scale from 0 to 10. We will report the median 16Mar2018

change in pain intensity of our patients who receive intranasal hydromorphone. Our secondary outcome of adverse events will be reported using descriptive statistics, i.e. the proportion of patients who experienced each type of adverse events. We will also be recording the time at which rescue analgesics are administered, and report the results as a Kaplan-Meier curve. For the purposes of this pilot study, we will enrol 40 patients, which has been previously demonstrated to be sufficient in similar pilot studies evaluating the analgesic efficacy of other medications.

Potential Risks:

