The risks associated with receiving intranasal hydromorphone are the same as if administered by another route (e.g. intravenous). There is a chance that the patient may not experience the same degree of pain relief that they may have experienced if they had received intravenous hydromorphone. However, patients will have their pain assessed as per usual standard care, and can receive additional required analgesics at any point in time if their pain relief is inadequate. The procedures involved in this study do not increase the risk for adverse events normally associated with receiving hydromorphone. Potential Benefits: Provide information regarding any anticipated benefits of participating in this research. There should be a rational description of why such benefits are expected based on current knowledge. If there is unlikely to be direct benefit to participants/subjects, describe benefits to society. Please note that elements of participation such as compensation, access to medical care, receiving study results, etc. are not considered benefits of Risks, Benefits & Monitoring THe most common adverse events reported by patients who have received intranasal hydromorphone include bad taste in mouth (21%), dizziness (14%), somnolence (15%), nausea (6%), and vomiting (2%). Except for bad taste in mouth, the incidence of these adverse events associated with intranasal hydromorphone were all less than that experienced by patients who received the same dose of intravenous hydromorphone (Coda et al. 2003)

Potential Benefits:

If the treating physician was going to initiate an intravenous line for the sole purpose of administering a parenteral opioid analgesic to treat the child's pain, one potential benefit is that receiving intranasal hydromorphone instead would spare the child a painful and distressing needle stick. Another benefit is that the patient may receive longer duration of analgesia than if they had received intranasal fentanyl, which is a commonly-administered parenteral opioid analgesic in the pediatric emergency department.

Alternatives:

An alternative to participation in this study is to choose not to participate, or to receive an opioid analgesic by an alternate route (e.g. oral, intramuscular, or intravenous).

Data and Safety Monitoring:

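### The Kaplan-Meier plan for rescue has no rule for ED discharge; if discharge is censored, the curve will read at or above the share of children actually rescued in the ED

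*Combined protocol and SAP*

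**What the plan says.** The analysis of rescue is one sentence in Statistical Procedures: "We will also be recording the time at which rescue analgesics are administered, and report the results as a Kaplan-Meier curve". It does not say which rescue counts as the event, how a child who leaves without rescue is treated, what the time horizon is, or whether numbers at risk will be shown.

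Study Procedures has pain scored serially "until 6 hours, the patient is discharged from the emergency department, or a non-IN hydromorphone rescue analgesic is administered". That wording governs pain scores, but no contact after discharge is described, so a child who has left cannot have a later rescue recorded. Discharge is not defined as going home, and admission or transfer is not excluded.

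There are two kinds of rescue in Study Procedures. The first is intranasal (IN): "At the 15- and 30-minute marks, the patient will undergo a first and second rescue IN hydromorphone assessment". The second is another analgesic: "This non-IN hydromorphone rescue analgesic will be considered after 60 minutes, and its administration will be determined at the discretion of the primary attending physician". Potential Risks, by contrast, says that patients "can receive additional required analgesics at any point in time if their pain relief is inadequate". Potential Benefits adds that "the patient may receive longer duration of analgesia than if they had received intranasal fentanyl".

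**The concern.** A child who leaves the ED without rescue can no longer have an ED rescue. Discharge is therefore a competing event for the outcome being plotted, and the plan has no rule for it. A standard Kaplan-Meier analysis would censor these children. The curve then estimates rescue in a setting where nobody leaves, on the assumption that those who left would have needed rescue at the same rate as those who stayed. That is a different quantity from the proportion of the 40 children who were rescued, and readers can easily take one for the other.

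Two further problems follow. The late part of the curve may rest on few children, depending on length of stay. The assumption behind censoring is also doubtful: in a population enrolled for moderate to severe acute pain, pain control plausibly influences when a child leaves. This last point is an inference; the documents do not state it.

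At stake is how the study describes later rescue. The curve is the only planned time-to-event output, and the protocol names longer analgesia as a possible benefit, so readers may use the curve to judge durability.

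**Working it through.** **Plan's own figure.** There is none to reproduce. The documents give no expected rescue rate, length of stay or precision target, and the sample of 40 rests on precedent. All rates below are assumptions.

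**1. The inequality.** At each rescue time let d be the number rescued and n the number still at risk.
- One minus Kaplan-Meier (1−KM) adds up S_R × d/n, where S_R falls only at rescues.
- The proportion rescued in the ED adds up S_all × d/n, where S_all falls at rescues and at discharges.

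S_R is never below S_all, so 1−KM is never below the proportion rescued. They are equal only if no child leaves before a later rescue. This does not depend on why children leave.

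**2. Size under independent rates.** Assume a rescue rate r and a discharge rate m per hour, constant and unrelated to each other, from 60 minutes to 6 hours (5 hours).
- 1−KM = 1 − exp(−5r)
- Cumulative incidence of rescue = r/(r+m) × [1 − exp(−5(r+m))]
- At risk at 6 hours = 40 × exp(−5(r+m))

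| r | m | 1−KM | Rescued in ED | At risk of 40 |
|---|---|---|---|---|
| 0.06 | 0.20 | 25.9% | 16.8% | 10.9 |
| 0.06 | 0.35 | 25.9% | 12.8% | 5.1 |
| 0.06 | 0.50 | 25.9% | 10.1% | 2.4 |
| 0.10 | 0.20 | 39.3% | 25.9% | 8.9 |
| 0.10 | 0.35 | 39.3% | 19.9% | 4.2 |
| 0.10 | 0.50 | 39.3% | 15.8% | 2.0 |

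First row: 1 − exp(−0.30) = 0.259; 0.06/0.26 × [1 − exp(−1.30)] = 0.231 × 0.727 = 0.168; 40 × exp(−1.30) = 10.9.

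The gap runs from 25.9 − 16.8 = 9.1 points to 39.3 − 15.8 = 23.5 points. With r = 0.10 and no early discharge it is zero: both figures are 39.3%, and about 24 of 40 remain at risk. With about 5 children at risk, one rescue lowers the curve by a fifth of its current height, yet adds only 1/40 = 2.5 points to the proportion actually rescued.

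**3. If discharge is related to pain control.** In a simulation of 400,000 children, half were well controlled (rescue 0.05 per hour) and half poorly controlled (0.30 per hour). The true 6-hour risk had all stayed is 0.5 × [1 − exp(−0.25)] + 0.5 × [1 − exp(−1.50)] = 0.5 × 0.221 + 0.5 × 0.777, or about 50%.

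| Who leaves sooner (discharge per hour, well / poorly controlled) | 1−KM | Rescued in ED | At risk of 40 |
|---|---|---|---|
| Well controlled (0.60 / 0.15) | 64% | 33.5% | 2.9 |
| Neither (0.35 / 0.35) | 50% | 27.5% | 3.5 |
| Poorly controlled (0.15 / 0.60), e.g. admission or transfer | 39% | 24.4% | 7.6 |

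Against the full-follow-up risk the bias can go either way. Against the share rescued in the ED, 1−KM is higher in all three cases, as step 1 requires.

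**The case against.** The strongest reply is that the first table compares two estimands and shows no bias. With independent rates, Kaplan-Meier is correct for its own target: 26% is the 6-hour risk had every child stayed. This stands, and the figures should be read as a difference in what is estimated.

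A reader might also infer that the curve must overstate the need for rescue over 6 hours because comfortable children go home first. The documents do not support that. They do not link discharge to pain control, give a length of stay, or restrict discharge to going home. If children in more pain leave first, the bias reverses.

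Nor does the plan state that discharge will be censored. If children who left were carried event-free to 6 hours, 1−KM at 6 hours would equal the proportion rescued and the gap would vanish. But that rule would have to be written down, and it amounts to reporting cumulative incidence.

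The curve is descriptive, is named as neither the primary nor the secondary outcome, and belongs to a single-arm pilot. By Greenwood's formula with the first table's rates, its 95% half-width at 6 hours would be about 18 to 34 points, wider than the gaps. That limits the practical weight of the point. It does not excuse the gap, which is systematic and would not shrink with more patients.

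Finally, cumulative incidence does not measure durability either. At a rescue rate of 0.10 per hour it falls from 39.3% to 13.9% as discharge rises from 0 to 0.6 per hour. This is a genuine drawback, and the label on the result must reflect it.

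**Conclusion.** The point holds in a limited form and is worth correcting before analysis. If discharge is censored, 1−KM will be at least as large as the share of children rescued in the ED. Under the assumed rates the excess is about 9 to 23.5 points, with about 2 to 11 of 40 children left at 6 hours. The inequality is certain given censoring; its size depends on rescue and discharge rates that the documents do not give. Bias for the 6-hour risk under full follow-up is plausible, but its direction is unknown.

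It would go too far to say that the curve cannot describe 6 hours. That depends on the unstated length of stay, and the plan never says the curve measures analgesia to 6 hours: that limit caps the pain scores. Serial pain scores also bear on duration, and the remark about fentanyl is a potential benefit, not an endpoint. The IN doses at 15 and 30 minutes are unlikely to be affected by discharge. The primary outcome analysis does not depend on this curve.

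**What to change.** In Statistical Procedures and the data collection form:
- Record the time of ED discharge and the disposition (home, admission, transfer).
- State that the event is the first non-IN rescue analgesic, and report IN rescue doses separately as proportions.
- Report the cumulative incidence of rescue with discharge as a competing event, together with the cumulative incidence of discharge without rescue and the numbers at risk over time.
- Describe the result as rescue during the ED stay, not as duration of analgesia.
- If a Kaplan-Meier curve is kept alongside, label it as assuming that discharge is unrelated to later need for rescue.
- Reconcile Study Procedures and Potential Risks on when additional analgesics may be given, because this sets when an event can occur.

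The cost is two data items and a few sentences, with no extra patients or visits. Discharge already ends pain scoring, but the documents do not say that its time is recorded, and the data collection form is not among them. The remaining drawback is that cumulative incidence depends on local ED throughput, so it should be compared with other sites only alongside the discharge curve.

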Principal Investigator: [name], MPH

Study Purpose and Rationale:

Hydromorphone is a commonly prescribed opioid analgesic that is used in both adults and children. It can be administered by the oral (PO) route, but is associated with poor bioavailability and slow time to onset of action. It can also be administered by the intramuscular (IM) or intravenous (IV) routes, but both require needle sticks, which children report to be their most feared medical procedure, and that which they find highly distressing. The intranasal (IN) route is a safe and effective way of administering opioid analgesics (e.g. fentanyl, sufentanil) in both adults and children. Although there have been studies evaluating the bioavailability, pharmacokinetics, clinical efficacy, and adverse events of IN hydromorphone in adults, IN hydromorphone has not been yet been studied in children. Given the safe and efficacious reports of IN hydromorphone in adults, and the potential benefits of administering hydromorphone by the IN route for children, we aim to conduct a pilot study to evaluate the efficacy of IN hydromorphone in reducing pain in children with acute pain who present to the pediatric emergency department.

Study Design:

This will be a pilot study, in which we will prospectively enroll a convenience sample of children who present with moderate to severe acute pain to the pediatric emergency department of a single institution.

Study Procedures:

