Data will be reviewed on an ongoing basis by the PI with each patient enrolled. On an ongoing basis, the investigators will monitor accrual of study subjects, assess adherence to study protocol, assess 16Mar2018 Page 3 of 4

data quality, and collect and review adverse events and other subject safety matters. We will submit to the IRB protocol deviations and any requested protocol modifications. A data safety monitoring board (DSMB) consisting of two physicians unrelated to the study will be formed to evaluate safety and adherence to the protocol (Drs. [name] and [name], Division of Pediatric Emergency Medicine). The first review will be conducted after the first 10 patients are enrolled, and then the DSMB will convene every 6 months until the study is completed.

Adverse Event Reporting: An adverse event is any untoward medical occurrence by a subject. For each patient, the investigators will evaluate adverse events after completion of enrollment. All unanticipated problems (i.e. unexpected events, outcomes, or occurrences, at least possibly related to the research, and suggest an increase in risk of harm to subjects or others) will be reported to the IRB. This reporting will be done promptly, but no later than one week after the occurrence or after the PI acquiring knowledge of the unanticipated problem, and will also be reported at time of continuing review. All data will be maintained on password-protected computers and in locked file cabinets in a locked room to which only authorized study personnel will have access. Only approved research staff will view the clinical information of children enrolled in this study. We will retain study records and documentation for 3 years after the last enrolled patient has completed all study procedures.

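### After the 10-patient review the DSMB meets only by the calendar, so with fast accrual the remaining 30 of 40 children could be dosed with no further scheduled DSMB review

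*Combined protocol and SAP*

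**What the plan says.** The Statistical Procedures section fixes the size of this single-arm pilot: "For the purposes of this pilot study, we will enrol 40 patients". The Data and Safety Monitoring section sets up a DSMB "consisting of two physicians unrelated to the study will be formed to evaluate safety and adherence to the protocol". Its timetable has two parts. The opening look is triggered by a patient count: "The first review will be conducted after the first 10 patients are enrolled". Every later look is triggered by the calendar: "and then the DSMB will convene every 6 months until the study is completed".

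Between meetings, "Data will be reviewed on an ongoing basis by the PI with each patient enrolled", and "the investigators will monitor accrual of study subjects" along with protocol adherence, data quality and adverse events. Protocol deviations go to the IRB. Under Adverse Event Reporting, unanticipated problems go to the IRB within one week and again at continuing review. To qualify, a problem must be unexpected, at least possibly related to the research, and suggestive of increased risk.

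No accrual rate or study duration is given. The documents describe no later count-based DSMB trigger, no enrolment pause for the first review and no ad hoc DSMB meeting, and nothing requires adverse events to be sent to the DSMB between meetings.

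**The concern.** The number of children exposed between two calendar-based reviews depends entirely on how fast they are recruited, and the plan does not say how fast that will be. The first review avoids this problem because it is triggered by a patient count; the later ones do not. In a study of 40, a six-month interval could contain most or all of the remaining enrolment.

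This matters because, in the words of Study Purpose and Rationale, "IN hydromorphone has not been yet been studied in children". The adverse-event percentages under Potential Risks come from a study in healthy volunteers, and the clinical safety statement that supports the dose concerns adults. Study Procedures also allows further IN doses after assessments at 15 and 30 minutes, so tolerance of repeat dosing is part of what the DSMB has to judge. Most of the paediatric safety information will come from patients 11 to 40. A DSMB meeting held after the last dose can still inform later work, but it can no longer protect the participants in this study.

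**Working it through.** The plan gives no derivation for its sample size, only precedent from similar pilots, so there is no stated figure to reproduce. The check is direct arithmetic.

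**Inputs from the documents.** Total 40 (Statistical Procedures); first review at 10 and later interval 6 months (Data and Safety Monitoring).

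**Assumptions.** Constant accrual of r per month, with r varied because it is not stated; each child dosed at enrolment; first review held when the 10th patient is enrolled, with the six-month clock starting then.

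**Step 1: threshold rate.** Remaining children = 40 − 10 = 30. The rate that uses them all up by the next meeting is 30 / 6 = 5 per month.

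**Step 2: exposure by assumed rate.** Children dosed by the month-6 meeting = min(30, 6r). Months to finish = 30 / r.

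| Assumed r per month | Months to finish | Dosed by month 6 | Further DSMB meetings strictly before last dose |
|---|---|---|---|
| 1 | 30 | 6 | 4 |
| 2 | 15 | 12 | 2 |
| 3 | 10 | 18 | 1 |
| 4 | 7.5 | 24 | 1 |
| 5 | 6 | 30 | 0 (last dose and meeting coincide) |
| 6 | 5 | 30 | 0 |
| 10 | 3 | 30 | 0 |

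**Step 3: effect of a delay.** If enrolment continues for L months while the first review is arranged, and the clock starts at that review, the threshold becomes 30 / (6 + L): 30 / 7 = 4.3 per month for a one-month delay and 30 / 8 = 3.75 for two months. The documents settle neither the pause nor the start of the clock.

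**Step 4: what 10 patients can show.** With 0 events in 10, the two-sided 95% Clopper-Pearson upper limit is 1 − 0.025^(1/10) = 30.8%. The one-sided 95% limit is 1 − 0.05^(1/10) = 25.9%.

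For illustration only, take an event with an assumed true rate of 5%. The chance that it is absent from the first 10 is 0.95^10 = 0.60. The chance that the first 10 are clean and the next 30 contain at least one event is 0.95^10 × (1 − 0.95^30) = 0.599 × 0.785 = 0.47. At an assumed 2% the latter figure is 0.817 × 0.455 = 0.37.

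**The case against.** The strongest case on the other side is that this is a small pilot that already has an outside DSMB, an early look at a quarter of the sample and periodic meetings afterwards. There is no contradiction and no wrong figure. Recruitment is a convenience sample at one site that needs physician referral, an available study-team member and consent, and nothing shows that 5 or more per month is likely. Below that rate at least one further meeting falls before the last dose. Children are monitored by pulse oximetry and interval vital signs, adverse events are assessed hourly, and the PI reviews every patient, so a serious event would not wait for a DSMB meeting to be noticed. All of this stands, and it limits the weight of the point. It does not remove the dependence on an unknown rate: even at 3 or 4 per month, 18 or 24 of the 40 children fall between two reviews.

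Four stronger readings are tempting, and the documents do not support them.

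- *No independent review at all after patient 10.* The IRB route remains. It is driven by events and restricted to unexpected problems, so a rising rate of known effects such as the somnolence or vomiting listed under Potential Risks need not reach it, but it is independent oversight.
- *The first use of this route in children.* The plan says it has not been studied in children, which is not the same as never used. It also cites usual paediatric intravenous dosing of the same drug.
- *A serious-event rate of 5% is to be expected.* The illustrative rates in the working are assumptions. The plan reports no serious adverse events in the adult clinical studies it relies on for the dose.
- *A count trigger by itself caps exposure.* Without a pause, enrolment continues while the review is arranged. At an assumed 10 per month and a one-month delay, 10 × 1 = 10 more children would be dosed before the meeting.

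**Conclusion.** The point holds as a cheap improvement to safety monitoring, not as an error in any stated figure. The lapse is in scheduled DSMB review only. It is complete above 5 per month under the assumptions set out in the working, and possibly at somewhat lower rates if the first review is delayed while enrolment continues. At slower accrual it is partial, and at 1 per month it is minor (6 children between meetings). Because the accrual rate is unstated, the plan cannot show which of these cases applies. A clean first 10 would still be compatible with a true event rate of roughly a quarter to just under a third, so the early look cannot stand in for later ones.

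**What to change.** In Data and Safety Monitoring, replace the sentence on the timing of reviews with: *The DSMB will review after 10, 20 and 30 patients have been enrolled, and at least every 6 months, whichever comes first.*

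This places a review trigger every 10 patients, where the present rule could leave up to 30 between reviews. The sponsor should also state whether each review is to be completed before enrolment continues, since only then is the number dosed between reviews strictly limited to 10, and from what date the six months run.

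The cost is up to about two extra short meetings of the two physicians already appointed. Above 5 per month, the reviews at 20 and 30 are both additional to what the present text would deliver before the last dose. At 2 per month, two further meetings already fall before the last dose (months 6 and 12), and the new rule also gives two (10 / 2 = 5 months apart, at months 5 and 10), so nothing is added. If enrolment is paused for each review, there is also some delay to recruitment. No new patients, staff or procedures are needed.
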